Each of the volunteers will have to be with 2 or 3 patients at the same time since some authors state that performing support to more than one patient can compensate for a poor relationship with another patient, as well as serve as support in the event of a patient's death (Moulton et al., 2013). The volunteer-patient sessions will be conducted in rooms set up for this purpose in the Carlos Santamaría building of the UPV/EHU. After each session with the patients, each volunteer will have to attend an individual session with the program coordinator [name] to discuss their emotions and reactions after performing the intervention. Psychological supervision of the volunteers is a fundamental part of avoiding retraumatization and the possible appearance of anxious-depressive symptoms (Giese-Davis et al., 2006). Likewise, volunteers will have to participate in group sessions every two months with the rest of the volunteers and the program coordinator [name] in order to strengthen group cohesion, resolve doubts, detect needs and carry out the necessary training.

The patients in this study will be 120 patients with various types of cancer from the Onkologikoa Foundation. Each patient will be matched with a volunteer depending on the type of tumor and medical treatment, since some authors state that for the support program to be effective, the volunteers must have had the same type of tumor and medical treatment as the patients (Pistrang et al., 2012). This is why it will be necessary to homogenize the group of volunteers as much as possible so that the sample of patients has as little variability as possible. The inclusion criteria are: having received the diagnosis of cancer in the last month; not having started medical treatment; the tumor type and medical treatment coinciding with any of the volunteers. The exclusion criteria are: relapse; suffering or having suffered from a serious mental disorder (according to DSM-V criteria). The recruitment of these patients will take place just after the diagnosis, and the professionals of the Onkologikoa Foundation will be in charge of offering this type of intervention to the patients who meet the inclusion criteria of the study.

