Those patients who are interested in participating will be informed about the present research project by the coordinator of the program and by the members of the research team of the Onkologikoa Foundation and it will be these same people who will be in charge of giving the information sheet and the informed consent, and of summoning each participant for the collection of data for the first evaluation. Each participant will be given an evaluation questionnaire of sociodemographic, clinical and psychological variables that he/she will have to bring completed for the day of the appointment. Also, each participant will be given four saliva collection bottles, which they will have to collect four times the day before their appointment. The times of collection of these saliva samples will be upon waking up, 30 minutes later, before lunch (between 13:00 and 13:30) and before dinner (between 20:00 and 20:30). The saliva samples will be collected by the program coordinator at the Onkologikoa Foundation and will be coded and managed by the Biobanko. Subsequently, they will be taken to the Psychobiology laboratory of the UPV/EHU for the determination of different biological variables. In addition,

participants will have to undergo a blood draw on the day of the appointment. The blood collection will be performed by a nurse member of the research team of the Onkologikoa Foundation. The blood samples will be coded and managed by the Biobanko. Subsequently, they will be transferred to the Psychobiology laboratory of the UPV/EHU for the determination of different biological variables.

After this first collection of clinical, psychological and biological data, patients will be randomly selected, through a balanced block randomization method, to be part of the experimental group 1 (EG1) or the experimental group (EG2). As this is a crossover design clinical trial, patients in GE1 will start the peer social support program before the start of medical treatment, while patients in GE2 will start the peer social support program after the end of medical treatment.

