## VARIABLES

The sociodemographic and clinical variables to be collected are: age, marital status, employment status, language, family situation, clinical history of interest, personal and family history of psychopathology, pharmacological, psychological and substance use treatment, tumor type, stage and medical treatment.

The psychological variables will be assessed by means of the following questionnaires: Big-5 brief personality questionnaire, HADS anxiety and depression questionnaire, COPE-28 coping questionnaire, brief illness perception questionnaire, MOS-SSS social support questionnaire, SF-12 quality of life questionnaire, resilience scale, ERQ emotional regulation scale and the program satisfaction questionnaire.

The biological variables to be determined are:

- In blood: levels of cytokines related to tumor development and inflammation (IL1 $\beta$ , IL-2, IL-6, IL-8, IL-10, IFN- $\gamma$  and TNF- $\alpha$ ); monoaminergic activity (tyrosine, phenylalanine, tryptophan, quinurenine, serotonin, quinurenic acid and 3HK) and IDO activity (through the tyrosine-kinurenine ratio).
- In saliva: the diurnal cortisol cycle and estrogen and testosterone levels.

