#### DATA ANALYSIS

The relationships between the variables collected will be analyzed with the SPSS version 22.0 statistical package and with the JMP 10 statistical package. In all the analyses performed, the following variables will be controlled: type and duration of medical treatment and pharmacological treatment. Repeated measures analyses will be performed to study the effect of the intrasubject support program. Also, in order to study the possible physiological and psychological differences between experimental groups 1 and 2, analysis of variance (ANOVA) will be carried out. Pearson's correlation coefficient will be used to analyze the relationships between the different physiological and psychological variables considered in this study. Several General Linear Models (GLM) analyses will be performed to determine the predictive value of each of the variables in the possible benefit obtained after the application of the program. To study the interactions in each of the GLM analyses performed, a simple regression analysis will be carried out.

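### The GLMs meant to establish predictive value cover about 37 to 41 candidate variables in at most 120 patients, with no restricted predictor set, multiplicity control, validation or optimism correction described

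*Combined protocol and SAP*

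**What the plan says.** The Data Analysis section is a single paragraph. On prediction it says: "Several General Linear Models (GLM) analyses will be performed to determine the predictive value of each of the variables in the possible benefit" obtained once the programme has been applied. Interactions found in these models are to be followed up by simple regression. Every analysis is to adjust for the type and length of medical treatment and for drug treatment.

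The candidate variables are those in the Variables section. There is a sociodemographic and clinical list ("The sociodemographic and clinical variables to be collected are: age, marital status, employment status, language, family situation, clinical history of interest" and further items), a set of questionnaires ("The psychological variables will be assessed by means of the following questionnaires: Big-5 brief personality questionnaire, HADS anxiety and depression questionnaire" and others), and the blood and saliva markers. The Methods section gives the sample: "The patients in this study will be 120 patients with various types of cancer".

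The plan does not say which variables enter which model, how many terms a model may have, at which evaluation predictors are measured, which outcome represents benefit, or which statistic expresses predictive value. It describes no selection rule, multiplicity control, shrinkage, internal validation or second sample.

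**The concern.** A variable's predictive value is a statement about patients who were not used to fit the model. A linear model fitted and assessed on the same patients gives a flattering answer, and the flattery grows with the number of terms relative to the number of patients. Searching many variables singly has a parallel problem, since the best of a long list looks good by chance.

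Both routes are open here. The section's own wording invites the results to be read as prediction, and nothing in the plan labels them exploratory. What is at stake is a published list of predictors and an R-squared that are partly or wholly noise.

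**Working it through.** The plan states no R-squared, alpha, power or sample-size calculation, so there is no figure of its own to reproduce. The check asks what the described analysis would return if no variable were associated with the outcome.

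**Inputs**
- Patients: n = 120 (Methods), before any loss. No dropout figure is given.
- Sociodemographic and clinical variables: 11 to 14, depending on whether the compound items on psychopathology history and on treatments are split (Variables).
- Questionnaires at one score each: 9, or 8 without programme satisfaction, which is recorded only after the programme and cannot be a baseline predictor.
- Biological variables: 7 cytokines + 7 monoaminergic markers + 1 IDO ratio + 3 in saliva (cortisol cycle counted once) = 18.
- Total: 11 + 8 + 18 = 37 at the low end; 14 + 9 + 18 = 41 at the high end. Type of medical treatment and drug treatment are in this count although they are also compulsory covariates.

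**Joint entry.** For ordinary least squares with p terms and no association, the expected unadjusted R-squared is p/(n − 1).

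| Terms in the model (n = 120) | Expected R-squared from noise |
|---|---|
| 1 | 1/119 = 0.8% |
| 5 | 5/119 = 4.2% |
| 10 | 10/119 = 8.4% |
| 15 | 15/119 = 12.6% |
| 37 | 37/119 = 31.1% |
| 39 | 39/119 = 32.8% |
| 41 | 41/119 = 34.5% |
| 60 (subscales or multi-category factors) | 60/119 = 50.4% |

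For p = 40 the 95% range of R-squared under no association is 22% to 46%. If 20% of patients were lost (an assumption; n = 96), the expectation at p = 40 becomes 40/95 = 42%.

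**Performance in new patients.** In 500 simulated data sets of pure noise with n = 120:
- p = 40: apparent R-squared averaged 0.33, adjusted R-squared about 0.00, and R-squared in new patients −0.51.
- p = 10: the three values were 0.09, 0.00 and −0.11.

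**One variable at a time.** Alpha is assumed to be 0.05.
- Expected chance findings per outcome: 37 × 0.05 = 1.85 to 41 × 0.05 = 2.05, so about 2.
- Chance of at least one, if the variables were independent: 1 − 0.95^39 = 86% (85% for 37 variables, 88% for 41).
- Each null variable explains 0.8% on average, but in simulation the best of about 40 explained about 5%, a correlation of about 0.22.

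The joint and one-at-a-time figures belong to alternative ways of carrying out the plan and should not be added together.

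**The case against.** The strongest reply is that the plan does not commit to the damaging version of the analysis. It says "Several General Linear Models (GLM) analyses will be performed", which fits small or single-variable models at least as well as one large model. A reader might infer that about a third of the variance will appear predicted by noise. That needs every variable in one model, at one degree of freedom each, judged by unadjusted R-squared, and the text states none of these. This stands: the one-third figure is conditional and belongs within the range shown.

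A reader might also take the noise to be about two thirds, by fitting within one group of 60 (39/59 = 66%). The documents do not support that. No section says the GLMs are run by group, and 60 per group is itself an assumption, since the plan says only that "patients will be randomly selected, through a balanced block randomization method".

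Next, F-tests and adjusted R-squared allow for the number of fitted terms. That is true, and the plan does not say which measure it will use. But neither accounts for choosing among many variables or models, and adjusted R-squared does not measure performance in new patients: it averaged about zero in the simulation while R-squared in new patients was −0.51. The absence of validation is inferred from silence; the plan does not rule it out.

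The noise share also shrinks if there is real signal. With an assumed true R-squared of 0.30, apparent R-squared at 39 terms would be roughly 0.30 + 0.70 × 0.328 = 0.53, less than half of it noise. It would therefore be too strong to say that nothing found will reproduce.

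The 86% needs independence, and the markers are not independent; the IDO ratio, for one, is built from two markers already counted. The expected count of about 2 does not need independence.

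Finally, a reader might infer that the programme will be targeted using these results. The Aims section covers effectiveness, biological effects and timing, and does not mention selecting patients for the programme. This is an ancillary analysis, and the consequence is limited to what is reported about predictors.

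**Conclusion.** The concern holds in conditional form. The plan sets out to determine predictive value for about 37 to 41 variables in at most 120 patients and describes nothing that would separate prediction from chance fit. Each way of carrying it out yields chance predictors. Joint entry of everything gives an apparent R-squared of about 31 to 34% under no association. Models of 1 to 15 terms give about 1 to 13%, and 60 terms about 50%. Single testing gives about 2 chance findings per outcome.

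These sizes assume no true association, no loss of patients, one term per variable (except in the 60-term case), unadjusted R-squared for the joint figures, and alpha of 0.05 for the single tests. Which figure applies cannot be settled from the documents, because the division of variables among models is not stated. The omission itself does not depend on that choice.

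**What to change.** In the Data Analysis section:

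1. Name in advance, for each outcome, a short list of predictors measured at evaluation 1, and enter them jointly with the covariates the section already requires. The length is a judgement. As a guide, noise alone gives 4.2% at 5 terms and 8.4% at 10, and the covariates count towards those terms.
2. Report predictive value as cross-validated or bootstrap optimism-corrected R-squared in place of apparent fit, repeating any selection step inside each resample.
3. Label results for all other variables as hypothesis-generating.
4. Describe the result as prediction of outcome or change. Baseline predictors of change do not separate patients helped by the programme from patients who would have improved anyway. A statement about who benefits needs a predictor-by-group term tested at evaluation 2, when, on the planned sequence, only EG1 has received the programme.

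The cost is analysis work and a few sentences of text, with no new data, visits or patients. The downside is a lower reported R-squared and fewer claimed predictors.
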